2.3. Hypotheses

Primary Hypotheses

All primary and secondary hypotheses must be met in order to satisfy the objective the study.

Primary Hypotheses	
Endpoint	Hypothesis
Monocular logMAR visual acuity	The Test lens will be non-inferior to the control lens with respect to Distance Monocular logMAR Visual Acuity at the 2-week follow-up evaluation. A non-inferiority margin of 0.05 logMAR and a superiority margin of 0 logMAR will be used.
Biomicroscopy	The Test lens will be non-inferior to the control lens with respect

	to the percentage of eyes with Grade 3 or higher Slit Lamp Findings (Biomicroscopy) across all follow-up visits (scheduled and unscheduled). A non-inferiority margin of 5% will be used.
Fit acceptance rate	The proportion of eyes with acceptable fit will be greater than 90% across all scheduled visits for all subjects wearing the Test lens. The fit acceptance rate of the control lens is not a primary endpoint.
Overall CLUE comfort	The Test lens will be non-inferior to the control lens with respect to CLUE Overall Comfort at the 2-week follow-up evaluation. A non-inferiority margin of -5 points will be used

Secondary Hypotheses

Secondary Hypotheses	
Endpoint	Hypothesis
Overall CLUE Vision	The Test lens will be non-inferior to the control lens with respect to CLUE Overall quality of vision at the 2-week follow-up evaluation. A non-inferiority margin of -5 points will be used.
Overall CLUE handling	The Test lens will be non-inferior to the control with respect to CLUE Handling at the 2-week follow-up evaluation. A non-inferiority margin of -5 points will be used.

Other Hypotheses

Other Observations	
Endpoint	Hypothesis
Lens Preferences	The Test lens will be superior to the control lens in all 5 of the following lens preference items at the 2-week follow-up evaluation of the second wearing period. 

Other Observations	
Endpoint	Hypothesis
Indoor Performance Measures	
The Test lens will be superior to the control lens in at least 2 of the following 4 indoor performance measure(s) at the 2-week follow-up evaluation.
 
Driving Performance Metrics	
The Test lens will be non-inferior to the control lens in both of the following driving performance metrics at the 2-week follow-up evaluation. A cumulative odds ratio margin of 0.67 will be used.
 
Outdoor Performance Measures	
The Test lens will be superior to the control lens in at least 2 of the following 4 outdoor performance measure(s) at the 2-week follow-up evaluation.
 

Justification of Clinical Margins

- A 5 point increase in an average CLUE score translates into 10% shift in the distribution of scores for a population of soft contact lens wearers¹.
- The cumulative odds ratio margin of 0.67 was selected since this corresponds to no more than a 10% difference in cumulative proportion between the Test and control groups.

3. TARGETED STUDY POPULATION

3.1. General Characteristics

Approximately 130 subjects will be enrolled to ensure that at least 120 subjects will complete the study. Enrolled subjects will be habitual wearers of spherical contact lenses. All subjects will be the age of 18 and ≤ 49 years old. Eligible presbyopes will be those that wear full distance contact lenses in both eyes, then wear reading glasses over them. Subjects will wear

the Test and Control contact lenses approximately 2 weeks each bilaterally on a daily wear (DW) basis, then wear either the Test or Control lens again for 2 weeks, for a total study duration of approximately 42 days (6 weeks) per subject.

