Wear and Replacement Schedules	Wear Schedule: daily wear (DW) Replacement Schedule: approximately 2 weeks
Objectives	The primary objective of this study is to demonstrate non-inferiority of the Test lens compared to the Control lens with respect to CLUE comfort, Slit Lamp Findings and Monocular logMAR Distance Visual Acuity. This study will also aim to show the Fit Acceptance rate is at least 90% in order to assess performance of the Test lens for eventual Design Validation and/or Claims studies.
Study Endpoints	Primary Endpoints: 
• Monocular logMAR distance visual acuity• Biomicroscopy• Fit acceptance rate• Overall CLUE comfort Secondary Endpoints: 
• Overall CLUE vision• Overall CLUE handling

[figure not shown]
Study Design	
This study is a randomized, 5-visit, partial subject-masked, 2×3 bilateral crossover, dispensing trial. The study lenses will be worn as daily wear (DW) for a period of 2 weeks each with one of the study lenses being worn twice. Each study lens is expected to be worn at least five (5) days per week for at least six (6) hours per day worn. There will be no washout period between study lenses.
 
See the flow chart at the end of the synopsis table for the schematic of the study visits and procedures of main observations.

Sample Size	
Approximately 130 eligible subjects will be enrolled and randomized into the study. Approximately 120 subjects are targeted to complete the study. A replacement subject may be enrolled if a subject discontinues from the study prematurely; the decision whether to enroll replacement subjects will be made by the joint agreement of the Investigator and Sponsor.

Study Duration	
Subjects will wear the Test and control lenses for 2 weeks each in random order with one of the study lenses being worn twice for a total of 6 weeks per subject. The enrollment period will be 2 weeks, making the entire study approximately 8 weeks in duration.

Anticipated Study Population	
Approximately 130 subjects will be enrolled to ensure that at least 120 subjects will complete the study. Enrolled subjects will be habitual wearers of spherical contact lenses. All subjects will be the age of ≥ 18 and ≤ 49.

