2.2. Endpoints

Primary Endpoints

The primary endpoints are as follows:

Biomicroscopy

Biomicroscopy will be assessed for each subject eye at all study visits (scheduled and unscheduled). The percentage of Grade 3 or higher slit lamp findings will be analyzed and will include corneal infiltrates.

Distance Monocular Contact Lens Visual Acuity

Distance monocular contact lens visual performance (logMAR) is assessed for each subject eye at the 2-week follow-up evaluation.

Fit Acceptance Rate

Acceptable lens fit will be assessed at all scheduled visits for each subject eye. Fit acceptance rate will be based on the lens fit acceptance of eyes wearing the Test lens only. Fit rates of the control lens will also be collected, but are not a primary endpoint.

CLUE Overall Comfort

Overall comfort scores are assessed using the Contact Lens User Experience (CLUE) questionnaire at the two-week follow-up. CLUE is a validated patient-reported outcomes questionnaire to assess patient-experience attributes of soft, disposable contact lenses (comfort, vision, handling, and packaging) in a contact-lens wearing population in the US, ages 18-65. Scores follow a normal distribution with a population average score of 60 (SD 20), where higher scores indicate a more favorable/positive response. (2016)¹.

Secondary Endpoints

The Secondary endpoints are as follows:

CLUE Overall Quality of Vision and Handling

Overall Quality of vision and handling scores are assessed using the Contact Lens User Experience (CLUE) questionnaire at the 2-week follow-up. CLUE is a validated patient-reported outcomes questionnaire to assess patient-experience attributes of soft, disposable contact lenses (comfort, vision, handling, and packaging) in a contact-lens wearing population in the US, ages 18-65. Scores follow a normal distribution with a population average score of 60 (SD 20), where higher scores indicate a more favorable/positive response (2016)¹.

Other Observations

Lens Preferences

Lens preferences will be assessed by patient reported outcome (PRO) questions regarding lens preference at the 2-week follow-up of the second wearing period. Subjects will be asked to choose for each preference item one of the following responses: Strongly Prefer the first lens, Prefer the first lens, no preference, prefer the second lens, strongly prefer the second lens. Lens preference questions consist of:

[REDACTED]

Driving Performance

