1.23	Subjective Lens Fit Assessment	
Subjective Assessment of the Lens Fit. If the fit is graded as unacceptable based on the criteria below, then the subject is discontinued from the study and will not be replaced.
 
 1. Limbal exposure in any gaze 2. Edge lift 3. Insufficient and/or excessive movement in all three movement categories
1.24	Continuance	
For the subject to continue in the study, they must meet all three of the following criteria:
 
 1. Snellen visual acuity is 20/30 or better OD and OS 2. The lens fit is acceptable OD and OS 3. Investigator approval. If the Investigator does not approve the dispensing of the first study lens, then the study is terminated for that subject.
1.25	Dispense	
The lenses will be dispensed for 6-8 days
 
 1. The subjects should wear their lenses similar to the inclusion criteria: ≥ 6 hours

Visit 1: Treatment 1 Lens Fitting		
Step	Procedure	Details
		
per day, ≥ 5 days per week.
 
 2. The lenses will be worn as daily wear only. 3. All subjects will be provided Opti-Free® PureMoist® to be used in a rub regime. 4. Preservative-free rewetting drops are permitted if needed. 5. A patient instruction booklet will be provided. 6. The lenses must be stored in the supplied case out of direct sunlight. 
Note 1: In the event a lens is lost or damaged, the subject will return to the investigator site for replacement (extra lenses cannot be given at the dispensing visit).
 
Note 2: The subject's habitual contact lenses cannot be worn at any time during the study.

VISIT 2

The follow-up will occur 6-8 days after the initial dispensing. The subjects must enter the visit wearing their study contact lenses.

Visit 2: Treatment 1 Follow-Up 1		
Step	Procedure	Details
2.1.	Adverse Events and Concomitant Medications Review	
Review the subject's concomitant medications and record any changes from the previous study visit.
 
Record any adverse events or medical history changes from the previous study visit.

2.2.	Wearing Time	Record the average wearing time and comfortable wearing time.
2.3.	Compliance	Confirm compliance with the prescribed wear schedule. Outdoor and total hours will be asked.
2.4.	Subject Reported Ocular Symptoms	Subjects will respond to a verbal open-ended symptoms questionnaire.

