The sample size calculation for distance monocular visual performance was performed assuming that there was no difference between the Test and Control lenses to achieve a minimum statistical power of 80%. Assuming a mean of 0 LogMAR, a standard deviation of 0.10 (based on historical ACUVUE® OASYS®) and a correlation between eye of 0.80, 2000 replicating trials were simulated for the repeated measurements from the multivariate normal distribution.

Acceptable Lens Fit

Acceptable lens fit is a binary response as y=1 if a subject eye has an acceptable fit and 0 otherwise. The common reference rate of 95% was selected for the sample size calculation, since this is considered to be a more conservative reference proportion. Assuming a correlation 0.80 between measurements within the same subject and period; and assuming a correlation of 0.50 between measurements within the same subject across periods. A total of 2000 replicating trials were simulated to estimate a sample size with a minimum statistical power of 80%.

Slit Lamp Findings

There was no Grade 3 or higher SLFs in any of the four historical studies. Therefore an incidence rate of 0.5% was chosen based on previous research literature^{3, 4}. Assuming a correlation 0.50 between measurements within the same subject and period; and assuming a correlation of 0.30 between measurements within the same subject across periods. A total of 2000 replicating trials were simulated to estimate a sample size with a minimum statistical power of 80%.

Table 7: Sample Size Estimates and Power Calculations for Primary Endpoints

Endpoint	Number per Subjects to Complete	Power
Distance Monocular Visual Acuity	40	>99%
SLFs Grade 3 or Higher	120	86%
Acceptable lens Fit	70	83%
CLUE Comfort	60	80%

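### At the planning fit rate of 95%, enrolling 130 does not ensure 120 completers, and the rules on replacing fit failures conflict; the effect on power is small

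*Combined protocol and SAP*

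**What the plan says.** Enrolment and completion: section 3.1 says "Approximately 130 subjects will be enrolled to ensure that at least 120 subjects will complete the study", and section 4.3 and the synopsis entry on the anticipated population say the same. The synopsis entry on sample size is softer: "Approximately 120 subjects are targeted to complete the study". Section 8.1 defines a completer as a subject who has completed all scheduled visits.

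Fit rule: section 7.2 repeats one fit step at steps 1.23, 2.8, 3.9, 3.22, 4.9, 4.22 and 5.8, whichever lens is worn. If the fit is unacceptable, "then the subject is discontinued from the study and will not be replaced". The continuance steps at each dispensing require acceptable fit in both eyes.

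Replacement: the synopsis says "A replacement subject may be enrolled if a subject discontinues from the study prematurely", subject to joint agreement of investigator and sponsor. Section 5.2 permits replacement of discontinued subjects. Section 8.2 requires discussion with the sponsor before additional subjects are enrolled after a premature discontinuation. None of the three excludes fit failures.

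Planning inputs for fit (section 14.2): "The common reference rate of 95% was selected for the sample size calculation", described there as conservative. The simulation takes 0.80 as the correlation within a subject and period, and 0.50 as the correlation within a subject from one period to another. The endpoint concerns one lens: "Fit acceptance rate will be based on the lens fit acceptance of eyes wearing the Test lens only" (section 2.2).

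Table 7 asks for 120 completers for Grade 3 or higher slit lamp findings (86% power), 70 for fit, 60 for CLUE comfort and 40 for visual acuity.

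**The concern.** The completer count is stated as something the enrolment figure secures, yet the protocol's own discontinuation rule and planning fit rate can use up the whole 10-subject allowance before any other loss. Those other losses are also written in: the 20/30 acuity criterion at each dispensing, Grade 3 slit lamp findings, corneal infiltrative events, missed visits and non-compliance with wear. The 120 comes from the slit lamp endpoint, and section 2.3 requires all primary and secondary hypotheses to be met.

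The replacement conflict matters separately. Fit is a primary endpoint, and sites have two instructions for the same event. If a fit failure were replaced and its result not carried into the analysis, the fit acceptance rate would be biased upwards.

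**Working it through.** **The plan's own figure.** No dropout rate is readable, so 130 cannot be derived. Backing it out gives (130 − 120)/130 = 7.7%.

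**One period, one assessment per eye.** With p = 0.95 and within-period correlation 0.80:

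P(both eyes acceptable) = p² + ρp(1 − p) = 0.9025 + 0.80 × 0.95 × 0.05 = 0.9405.

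So 5.95% of subjects fail, or 0.0595 × 130 = 7.7 of the 10 allowed.

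**Three periods, both lenses at 95%.** Simple bounds are 130 × 0.9405 = 122.3 left if periods are perfectly correlated and 130 × 0.9405³ = 108.1 if they are independent. With the plan's 0.50 across periods, read as a correlation of the binary outcomes, simulation gives a failure probability of 0.0862 over two periods and 0.1039 over three:

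- Both lenses at 95%: 130 × (1 − 0.1039) = 116.5 (116.0 under a second model with the same correlations).
- Test lens only at 95%, Control never failing. A subject has one Test period in one sequence and two in the other, so the failure rate is (0.0595 + 0.0862)/2 = 0.0729, and 130 × (1 − 0.0729) = 120.5.

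**All scheduled assessments.** Section 7.2 schedules seven assessments: 3, 2 and 2 by period. A failure at Visit 5 may not prevent completion, so six is also shown. Expected subjects left of 130, from fit failures alone:

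| Test / Control fit rate | One per period | Six (to Visit 4 fitting) | All seven |
|---|---|---|---|
| 95% / 95% | 116.0–116.5 | 114.9 | 114.4 |
| 95% / 97% | 118.6 | 117.6 | – |
| 95% / about 100% | 120.5 | 119.2 | 118.8 |
| 97% / 97% | 121.7 | 120.7 | – |
| 98% / 98% | 124.4 | 123.8 | – |

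**Chance of keeping at least 120 of 130** (binomial, fit failures only): about 0.65 in the mildest 95% case (Test only, one assessment per period), 0.43 for Test only with seven assessments, about 0.20 for both lenses with one per period, and 0.08 for both lenses with seven.

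**Sensitivity.** If 0.80 and 0.50 are read as correlations of an underlying normal variable, one assessment per period leaves 108.3 (both lenses at 95%) or 116.8 (Test only).

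**Effect on slit lamp power.** Take Table 7's 86% at 120 as given and scale by the normal approximation at one-sided 2.5%:

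power(n) = Φ[(1.960 + 1.080) × √(n/120) − 1.960].

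- n = 117: Φ(3.002 − 1.960) = Φ(1.042) = 85.1%.
- n = 115: Φ(2.976 − 1.960) = Φ(1.016) = 84.5%.
- n = 102: Φ(2.803 − 1.960) = Φ(0.843) = 80.0%.

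The scaling is rough for an outcome with an assumed incidence of 0.5%.

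**The case against.** The strongest reply is that 95% is not a forecast of attrition. It is a conservative rate for powering an endpoint defined on the Test lens only. Historical accountability and fit data exist for the same lenses, but those tables are not readable here, and they may well be the basis for 130. This stands, and it is why the result is given as a range. A reader might infer that a loss to about 115 follows directly from the plan's own rate. It does not, because that figure also needs the Control lens at 95%.

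A reader might also infer that both lenses must reach about 97% for 120 to remain. The documents do not support that threshold: with one assessment per period, Test at 95% and Control at 99% leaves 120.2.

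Nor does the trial become underpowered. Table 7 exceeds the 80% minimum at 120, scaled power stays above it down to about 102 completers, and the other primary endpoints need 40 to 70. Non-completers can still contribute slit lamp data, since that endpoint covers all follow-up visits.

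On replacement, the visit steps can be read as a specific exception to a discretionary general rule, and the sentence in section 5.2 sits in a paragraph on unmasking. That reading is possible, but no section states it. Losses for reasons other than fit may be replaceable, so they need not all count against a fixed 130. Even so, at 95% no reading makes 120 assured.

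**Conclusion.** The point holds in limited form. At the planning rate of 95% and the stated correlations, fit failures alone leave an expected 114 to 117 of 130 if the rate applies to both lenses, and 119 to 120.5 if it applies to Test only. Even the mildest of these cases gives only about a 65% chance of 120 before any other loss. With both lenses at 98%, about 124 remain, which leaves room for about four other losses. The figures rest on the binary reading of the correlations, on the across-period correlation also holding between different lenses, and on an assumed Control rate.

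The replacement wording is inconsistent as written and must be reconciled. The consequence for power is small, roughly one to two percentage points on the slit lamp endpoint, so this concerns the accuracy of the stated completer number and the handling of fit failures. It does not show that the sample size is inadequate.

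**What to change.** 1. In the synopsis, 3.1 and 4.3, replace the assurance of at least 120 completers with an expected range. State the fit rates and other-loss rates behind it, with the Control rate taken from the historical tables or labelled as an assumption.
2. In Table 7, add the slit lamp power at the lower end of that range, using the existing simulation.
3. Reconcile the replacement wording in the synopsis, 5.2, 8.2 and the fit steps 1.23 to 5.8, so that one rule for fit failures appears throughout.
4. State that a subject discontinued for unacceptable fit, replaced or not, keeps that result in the fit acceptance analysis. Section 8.1 restricts the analysis sets to dispensed subjects, which would drop a failure at the Visit 1 fitting, although the safety and intent-to-treat definitions in 14.3 are wider.

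The cost is one rerun of the simulation, edits to wording, and a slightly less favourable completer number and power.

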3.2. Inclusion Criteria

Potential subjects must satisfy all of the following criteria to be enrolled in the study:

1. The subject must read and sign the Informed Consent form.
2. The subject must appear able and willing to adhere to the instructions set forth in this clinical protocol.
3. Healthy adult males or females age ≥ 18 and ≤ 49 years of age with signed informed consent. Eligible presbyopes will be those that wear full distance contact lenses in both eyes, then wear reading glasses over them.
4. The subject's optimal vertexed spherical equivalent distance correction must be between -1.00 and -6.00D.
5. The subject's refractive cylinder must be ≤ 1.00 D in each eye.
6. The subject must have visual acuity best correctable to 20/25+3 or better for each eye.
7. Subjects must own a wearable pair of spectacles.
8. The subject is a current spherical soft contact lens wearer (defined as a minimum of 6 hours of DW per day, at least 5 days per week, for a minimum of 1 month prior to the study) and willing to wear the study lenses on a similar basis.
9. Subjects must be able and willing to wear the study lenses at least 6 hours a day, a minimum of 5 days per week
10. The subject must have normal eyes (i.e., no ocular medications or infections of any type).

3.3. Exclusion Criteria

Potential subjects who meet any of the following criteria will be excluded from participating in the study:

1. Currently pregnant or lactating (subjects who become pregnant during the study will be discontinued).
2. Any systemic disease, autoimmune disease, or use of medication, which may interfere with contact lens wear. This may include, but not be limited to, diabetes, hyperthyroidism, recurrent herpes simplex/zoster, Sjögren's syndrome, xerophthalmia, acne rosacea, Stevens-Johnson syndrome, and immunosuppressive diseases or any infectious diseases (e.g. hepatitis, tuberculosis).
3. Use of any of the following medications within 1 week prior to enrollment: oral retinoid isotretinoin (e.g. Accutane), oral tetracyclines, topical scopolamine, oral (e.g. Seldane, Chlor-Trimeton, and Benadryl) and ophthalmic antihistamines, oral phenothiazines (e.g., Haldol, Mellaril, Thorazine, Elavil, Pamelor, Compazine), oral and ophthalmic Beta-adrenergic blockers (e.g., Propranolol, Timolol, and Practolol), systemic steroids, and any prescribed or over the counter (OTC) ocular medication.
4. Entropion, ectropion, extrusions, chalazia, recurrent styes, glaucoma, history of recurrent corneal erosions, aphakia, or moderate or above corneal distortion.

5. Any previous, or planned, ocular or interocular surgery (e.g., radial keratotomy, PRK, LASIK, etc.).
6. Any Grade 3 or greater slit lamp findings (e.g., edema, corneal neovascularization, corneal staining, tarsal abnormalities, conjunctival injection) on the FDA classification scale, any previous history or signs of a contact lens-related corneal inflammatory event (e.g., past peripheral ulcer or round peripheral scar), or any other ocular abnormality that may contraindicate contact lens wear.
7. Any known hypersensitivity or allergic reaction to Optifree®PureMoist® multi-purpose care solution or Eye-Cept® rewetting drop solution
8. Any ocular infection, allergy or clinically significant ocular disease (e.g. corneal edema, uveitis, severe keratoconjunctivitis sicca, ocular hypertension), or ocular conditions (e.g. strabismus), which might interfere with the study.
9. Any corneal distortion resulting from previous hard or rigid gas permeable contact lens wear.
10. Toric, extended wear, monovision or multi-focal contact lens correction.
11. Participation in any contact lens or lens care product clinical trial within 30 days prior to study enrollment.
12. Participation in clinical trials involving the Test lens within 3 months prior to study enrollment.
13. History of binocular vision abnormality or strabismus.
14. Employee, relative or friends of employees of any ophthalmic company, or investigational clinic (e.g., Investigator, Coordinator, Technician).

